# Adverse Reaction (AR)

An AR is any harmful and unintended reaction to an investigational drug, regardless of the dose administered.

# Serious Adverse Event (SAE) and Serious Adverse Reaction (SAR)

AEs or ARs are considered serious that, at any dose, can cause death, threaten the life of the subject, require hospitalization of the patient or prolong an existing hospitalization, cause permanent or significant disability or disability, or give rise to an anomaly or malformation congenital. Suspicions of AE or AR that are medically important, even if they do not meet the above criteria, are also considered serious, including important medical events that require intervention to prevent one of the consequences described above from occurring. Likewise, all suspicions of transmission of an infectious agent through a drug will be reported as serious.

The concept "threatening the life of the subject" in the definition refers to the fact that, in the opinion of the researcher, the patient at the time of AE or AR is at real risk of death; It does not refer to the hypothetical AE / AR could have caused death if it had been more intense.

The concept "require hospitalization" will exclude both planned hospitalizations for scheduled treatments and those that have been planned or anticipated prior to commencing the study in relation to a pre-existing medical situation.

# **Unexpected Adverse Reaction**

Any AR whose nature, intensity or consequences do not correspond to the referenced security information.

# **Serious and Unexpected Adverse Reaction**

SAR (previously defined), the nature, severity or consequences of which do not correspond to the reference security information.

# **Causality Criteria**

- Related AE: The temporal relationship of AE with the study medication indicates a possible causal relationship and cannot be explained by factors such as the patient's clinical status, therapeutic interventions.
- Unrelated AE: The temporal relationship of AE with study medication indicates an unlikely causal relationship, or other factors (medication or concomitant conditions), other therapeutic interventions provide a satisfactory explanation for AE

For expedited notification purposes, the following categories will be considered **related**: highly probable, probable and not clearly attributable; and as **unrelated**, the improbable, excluded and impossible to assess category.

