# 6.1.2 Secondary endpoint

Secondary endpoints consist of improvement in the severity of negative symptoms as measured by the change in severity of negative symptoms on the SANS and NSA-4 score over the visits of each period (frame time: baseline visit, week 4, week 12, week 24, week 26, week 30, week 38 and week 50).

- Additionally the following secondary objectives will be evaluated. Functional
  improvement due to the change in general functioning measured by the GAF
  scale score from the beginning to week 24 of each period (frame time:
  baseline visit, week 12, week 24, week 26, week 38 and week 50)
- Safety assessment by measuring the frequency, severity, and relationship with study medication of any adverse event described during treatment. The reasons for withdrawal and / or abandonment of the trial will also be evaluated (if applicable): from the signing of the IC until week 52.

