#### 8.- TREATMENT OF SUBJECTS

## **Experimental Group**

The experimental group will be based on including Vortioxetine as an adjunct drug to the usual antipsychotic treatment that the subject is taking.

The route of administration of vortioxetine is oral in a single daily dose.

It will start with 10 mg / day for the first 2 weeks, followed by 20 mg / day for the remainder of the study. The vortioxetine dose may be reduced to 5 mg or 10 mg for reasons of tolerability at the discretion of the physician.

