# 11.4 Information of Adverse Events

The investigator will monitor and systematically collect the AEs related to study medication (ARs) starting from the signing of the Informed Consent Form until the final follow-up visit of each subject.

Also, the investigator will assess and record, in detail, the AR, including the start and dates, the description of the event, severity, course, outcome, and the measures taken (treatments, additional complementary examinations, etc).

The AR will be recorded in the medical history and recorded in the Case Report Form.

The subjects who present an AR will be subjected to relevant follow-up until duration of the same.

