# **ANNEX II. SAE NOTIFICATION FORM**

# (Fundación Pública Andaluza para la Gestión de la Investigación en Salud de Sevilla)

(2021-001333-38 / CAVES)

	FAX: [name]	rso Grave 38 deandalucia		
Tipo de informe:	cial 🗌	De	Sagui	miento 🗌		
ripo de informe.	ан 🗌	De	Segui	memb		
1. Datos del centro del estudio						
Número de centro:			País:			
Nombre del investigador principal:			Nomb	ore del Notifica	dor:	
Firma del investigador:						
2. Datos del paciente						
Número de Paciente (número de selección y/o asignación al azar)	Año de Nacimiento		Sexo	Atura (cm)	Peso (kg)	
	AAAA		M V			
Evento Adverso Grave/ Evento A esta página)	dverso de e	spec	ial int	erés (para repo	rtar eventos adi	icionales copiar
Término del Evento (Agrupar los sín diagnóstico, para ser consistente con		un úr	nico	Fecha de in	icio (DD / MM	/ AAAA)
Descripción del evento (evolución de relevantes, las contramedidas, los faces de la contramedida de la contr	tores de con					s hallazgos
	ro f					
Sí No						

NOMBRE DEL ESTUDI DE ENSAY		NÚMERO DE CENTR		O NÚN		MERO DE PACIENT	E
4. Gravedad del EAG		5. Crite graveda		6. Evolución del evento (en el momento del informe)			
Muerte Riesgo inmediato par Hospitalización/ Hospitalización Discapacidad/ Incapa Anomalías congénita Medicamente signific	prolongació acidad funciona s	n Sev	derado	fech	Recuper Recuper Recuper 1a: No recup Muerte 1a: Se des co	ándos e ado con secuelas perado	
7. Fase del estudio en e	el momento de	el evento					
Cribado Lavado Otra, por favor es peo	ificar:		Tratami				
8. Información del prod	luoto						
Producto del	Dosis /	recuencia	Fecha admin (DD / MI	istrac	ión	Fecha última administració (DD / MM / AAA	ón
9. Evaluación de la causalidad	10. Acción o producto co evento						1
Muy probable Probable No claramente atribuible Improbable Excluida Imposible de evaluar	Reducci Disconti permanente No aplic	Dis emente able	dosis temporalmente Discontinuado		Retirada: ¿El evento desapareció tras dejar de utilizar el producto?  Sí No N/A  Se des conoce  Reexposición: ¿Reaparición del evento tras la reintroducción del producto?  Sí No N/A  Se des conoce		
12. Desenmascaramien	to						
¿Se rompió el código de En caso afirmativo, propo		_	No ☐ Sí				

13	. Medicación Conco	mitante	Sí 🔲	No 🗌		Produc	to sos	pednoso: 1 🔲 :	2 3 4 5		
UΤ	ILIZADA EN EL MOME	NTO DE	EAG	Exduir	aquellos	producto	s utiliz				
	Nombre comercial/ Principio activo			Ruta	uta Indica		Fecha de inic DD / MM / AAAA	io Fecha de fir DD / MM / AAAA			

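### Section 11.2 lets a satisfactory alternative explanation make an adverse event unrelated even when vortioxetine may have contributed, and its definitions do not match its own expedited-notification list

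*Protocol*

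**What the plan says.** Protocol section 11.2, under Causality Criteria, gives two definitions. A related event is one whose timing "indicates a possible causal relationship and cannot be explained by factors such as the patient's clinical status, therapeutic interventions". An unrelated event is one whose timing makes causality unlikely, "or other factors (medication or concomitant conditions), other therapeutic interventions provide a satisfactory explanation for AE".

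The same section then sorts six causality categories for expedited notification. Those counted as related are "highly probable, probable and not clearly attributable". Those counted as unrelated are "the improbable, excluded and impossible to assess category". The six grades match the causality field of the serious adverse event form in Annex II: "Muy probable Probable No claramente atribuible Improbable Excluida Imposible de evaluar".

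Section 8 describes the experimental treatment as "including Vortioxetine as an adjunct drug to the usual antipsychotic treatment that the subject is taking". The safety endpoint in section 6.1.2 includes the "relationship with study medication of any adverse event described during treatment".

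**The concern.** Relatedness to vortioxetine is judged in patients who all take an antipsychotic as well and all have a chronic psychiatric illness. Section 8.2.1 also allows benzodiazepines. A causality rule for an add-on drug has to deal with events to which both drugs may contribute. Section 11.2 does not: once another drug or condition explains the event satisfactorily, the event is unrelated, whether or not vortioxetine may also have played a part.

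The label has consequences. It is part of the safety endpoint (6.1.2). Section 11.4 directs the investigator to "systematically collect the AEs related to study medication (ARs"), so collection there depends on it. The 24-hour instruction that opens section 11.5 is worded for serious events that are both related and unexpected. If two rules in one section can label the same event differently, the endpoint table and the expedited reports may not agree.

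**Working it through.** The protocol states no figure on this point, so the check is logical: set the definitions against the category list, case by case.

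**Structure of the rules (section 11.2)**

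- *Related* joins two conditions with *and*: the timing fits, and the event cannot be explained otherwise.
- *Unrelated* joins two conditions with *or*: the timing is unlikely, or something else explains the event satisfactorily.
- The list assigns three grades to each side, for expedited notification only.

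| Case | By the definitions | By the list |
|---|---|---|
| A. Timing fits, no other explanation | Related | Related, if given any of the three related grades |
| B. Timing fits, antipsychotic or illness explains it satisfactorily, vortioxetine contribution not excluded | Unrelated | Related, if graded *not clearly attributable* |
| C. Timing fits, another explanation is possible but not satisfactory | Undecided: not clearly unrelated, and arguably not related | Related, if graded *not clearly attributable* |
| D. Impossible to assess | Unrelated is not met, since no alternative has been established | Unrelated |
| E. Timing unlikely | Unrelated | Unrelated, if graded *improbable* or *excluded* |

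**Reading the table**

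1. Only A and E are free of difficulty.
2. Case B shows the problem in the definition. The timing favours vortioxetine and a contribution is not ruled out, yet the *or* limb settles the matter. Neither definition has a place for joint causation or for an effect of the combination.
3. Case B also shows the conflict: unrelated by definition, related by list if given the middle grade.
4. Case C falls between the definitions, because one requires that no explanation exists and the other requires a satisfactory one.
5. Case D is a second mismatch, in the opposite direction.
6. No text links the six grades to the two definitions. The list is confined to expedited notification and the form to serious events, so for non-serious events only the two definitions apply.

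**How often case B could arise.** Section 8 makes the antipsychotic a constant companion of vortioxetine, so a candidate alternative is present throughout exposure. Being present is not the same as being a satisfactory explanation. The protocol gives no rate of vortioxetine reactions and no basis for the share that an assessor would ascribe to something else, so the number of changed labels cannot be calculated.

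**The case against.** The strongest reply has five parts.

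- **The threshold is *satisfactory*, not *possible*.** A reader might infer that any event with another conceivable cause becomes unrelated. The text does not say so; a merely possible alternative falls into the gap of case C. This stands, and it limits the point to events with a satisfactory alternative.
- **Stable background.** Section 7.1 requires stable antipsychotic doses for at least 4 weeks and low symptom and movement scores, and section 2.16 requires at least 3 months of clinical stability. A new event after vortioxetine starts is then not easily blamed on a long-standing drug or a stable illness. This reduces how often case B arises, and it defeats the inference that every event on vortioxetine has a ready excuse. It does not remove the problem: these are entry conditions, I find no section that fixes the antipsychotic afterwards, and stability does not rule out an effect of the combination.
- **Direction of bias.** A reader might infer that the rule can only make vortioxetine look safer. The *or* limb does work that way. But the trial is open-label (section 6.4), and an assessor may equally over-attribute events to the newly added drug. The protocol does not determine the net direction.
- **Protection of expedited reporting.** The list is the specific rule for that purpose and takes the cautious side on *not clearly attributable*. The protocol does not define that grade, so the conflict in case B depends on the assessor using it there. Annex II also records withdrawal, re-exposure and a suspected concomitant drug. This partly protects serious events that are graded on the form; it does nothing for non-serious events.
- **Lost events.** A reader might infer that events labelled unrelated go unrecorded because of section 11.2. That would follow from the wording of section 11.4, which is a separate matter. Section 6.1.2 covers any adverse event, and the section 9 schedule lists adverse events at every visit from Visit 3. The consequence of section 11.2 itself is a wrong or inconsistent label.

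**Conclusion.** The point holds in a limited form. Section 11.2 lets a satisfactory alternative explanation, including background medication or a concomitant condition, make an event unrelated although its timing fits vortioxetine and a contribution is not excluded. Its definitions and its category list are not reconciled: case B can be labelled both ways, and case C fits neither definition clearly. Some vortioxetine reactions can therefore be classed as unrelated; that they will be is a matter of the assessor's judgement.

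No numerical size can be given, because any illustration would rest on an assumed reaction rate and an assumed share of relabelled events. The conclusion assumes that study medication in section 11.2 means vortioxetine and, for the conflict in case B, that *not clearly attributable* is used for events with competing causes, which is its natural meaning. The primary cognitive endpoint is not affected. The safety endpoint and the consistency of serious event reporting are, which is enough to justify the small correction.

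**What to change.** Revise the Causality Criteria paragraph in section 11.2:

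1. Define a related event as one for which, given its timing, there is a reasonable possibility that vortioxetine contributed, alone or in combination with other treatment.
2. Do not let the presence of another candidate cause decide *unrelated*. Keep that label for events whose timing makes a contribution unlikely or for which a documented other cause excludes one. This is stricter than the present rule, under which a satisfactory alternative is enough even if vortioxetine also contributed.
3. Record a suspected concomitant drug in addition to the vortioxetine assessment, not in its place. Annex II already has the field for serious events; add a matching instruction to the case report form.
4. State one mapping of the six Annex II grades to related and unrelated, with *not clearly attributable* as related and an explicit, reasoned place for *impossible to assess*. Use it for adverse event assessment, serious event and SUSAR reporting, and the safety endpoint.

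The cost is one paragraph of protocol text and one case report form instruction. The downside is that a few more events, some really due to the antipsychotic, will be classed as related, and a few more reports will be assessed for expedited notification.

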#### 11.5 Notification and collection of serious adverse events

The principal investigator or a collaborator must report to the Pharmacovigilance (PhV) department PhV -UICEC-HUVR, all serious adverse events (as defined below), which are related to the treatment and unexpected (SUSAR), within 24 hours (one business day), as of its knowledge (Annex II). Serious adverse events that occur should be reported at any time from the patient's inclusion in the study (defined as the time the subject signs the informed consent) and up to 30 days after the subject concludes or leaves the study. A subject is considered complete either after the conclusion of the last visit or contact (telephone contact with the investigator or a collaborator), as indicated in the protocol evaluation schedule, or after the last dose study medication, whichever occurs later. Withdrawal is defined as the date a subject and / or the investigator determine that the subject can no longer meet the study requirements at any subsequent visits and evaluations.

The investigator will complete and sign the SAEs notification form (Annex II) that will be sent by fax or email to:

Unidad de Investigación Clínica y Ensayos Clínicos Hospital Universitario Virgen del Rocío Dpto. Farmacovigilancia

Email: [contact]

[name] [contact] [contact]

PhV staff will review the form received and, if applicable, will request additional information from the investigator. The researcher will provide information to the promoter or whoever assumes the tasks delegated by the promoter (PhV-UICEC-HUVR Unit) whenever requested and, in any case, when his initial assessment regarding severity or causality changes. To communicate the follow-up information, the notification procedure described previously will be followed.

The PhV-UICEC-HUVR staff will keep a detailed record of all the SUSARs, pregnancies, medications errors, etc. that are communicated to them by the researchers.

Each SUSAR, pregnancy or medication error communicated to the Promoter's PharmacoVigilance team will be reported to the LundBeck laboratory within 24 hours of being aware of it., to the email: [contact]

In the event that a medication error occurs or the investigational medication is used outside of the protocol provided during the study, the investigator will notify the PhV-UICEC-HUVR within 24 hours of being aware of it. The circuit for notification and the form will be the same as for SAEs.

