1.											
2.											
3.											
4.											
5.											
Me	dicación concomit	ante sos	pecho	sa: Si	el EAG	está caus	ado p	or uno de los pro	oductos mencionad		
am	iba, porfavormarque la	casilla co	nrespor	ndiente (	en el enc	abezado	del ap	artado.			
14	. Información médio	a releva	nte (E į	alergi	as, disfu	nción rer	na Vh e	pática) Sí	No		
	Condición / Enfermedad							cha de inicio	Fecha de fin		
							DD	/ MM / AAAA	DD / MM / AAA		
1.											
2.	2.										
3.	3.										
4.											
15	5. Hospitalización (c	om pletai	si pro	cede)	16	Muerte	(com	pletar, si proce	de)		
_	Nueva hospitalizad		,,,,,,,,,,,,,,,,,,,,,,,,,,,,,,,,,,,,,,,			Fecha:					
ᅡ	Prolongación de la					Causa(s) principal de muerte:					
╙	_ Prolongación de la	nospitai	izacion	1	100	Causa(s) principarde muerte.					
F	echa de admisión:				-						
_					<del>-</del>		7.00				
F	echa de alta:				- 1	Autopsia: Sí No (en caso afirm ativo, por favor adjuntar el inform e)					
					(=						
_											
17	7. Información adici	onal (Co	ntinúe	en una	página	adiciona	lsi es	necesario)			
					7-5			,			

SEND IMMEDIATELY (24 hours after knowledge) BY FAX TO THE PHARMACOVIGILANCE TEAM OF THE RESEARCH AND CLINICAL TRIALS UNIT OF THE VIRGEN DEL ROCÍO UNIVERSITY HOSPITAL (UICEC-HUVR).

([contact])

Email: [contact]

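### Serious events whose causality cannot be assessed are treated as unrelated for expedited notification, although they do not meet the protocol's definition of unrelated, and the 24-hour reporting deadline is stated in two incompatible ways

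*Protocol*

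**What the plan says.** **Causality.** Under Causality Criteria, section 11.2 of the protocol first defines two classes.

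- A related event is one whose timing "indicates a possible causal relationship and cannot be explained by factors such as the patient's clinical status" or by therapeutic interventions.
- An unrelated event can qualify in two ways. Either "The temporal relationship of AE with study medication indicates an unlikely causal relationship", or other medication, concomitant conditions or "other therapeutic interventions provide a satisfactory explanation for AE".

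A further sentence, limited to expedited notification, sorts six finer categories into these two classes. Related takes "highly probable, probable and not clearly attributable". Unrelated takes "the improbable, excluded and impossible to assess category". The SAE form in Annex II offers the same six categories as tick boxes, so an investigator can choose the unassessable one.

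**Routing.** Section 11.5 tells the investigator to send pharmacovigilance the serious events that are both related and unexpected. It then says, with no condition on relatedness, that serious adverse events should be reported from consent until 30 days after the subject leaves or completes the study. SUSARs are passed to the manufacturer within 24 hours (11.5). They go to the authorities within 15 calendar days, or 7 if fatal or life-threatening, counted from the sponsor's awareness (11.6).

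**Deadline.** Section 11.5 gives the investigator's limit as "within 24 hours (one business day". The Annex II form says "SEND IMMEDIATELY (24 hours after knowledge".

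**The concern.** A rating of unassessable means that the information does not allow a judgement. Treating that as a finding of no relationship takes the event out of the SUSAR definition without anyone having judged the drug an unlikely cause. The protocol gives no reason for counting one uncertain category as related and the other as unrelated, and it states no default for events that are waiting for more information.

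At stake is the expedited route to the authorities and to the manufacturer for serious unexpected events with little information. The deadline wording is a smaller problem of the same kind: the protocol can be followed to the letter while a report arrives later than the SAE form allows.

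**Working it through.** **1. Testing the unassessable category against the definitions in 11.2**

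| Test | What it requires | Does an unassessable event meet it? |
|---|---|---|
| Unrelated, first limb | A judgement that causality is unlikely | No, no judgement could be made |
| Unrelated, second limb | A satisfactory other explanation | No, none has been established |
| Related | Possible causality, not explained by other factors | Not clearly |

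The definitions therefore leave the category unclassified. Only the expedited-notification sentence decides its class, and it chooses unrelated.

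**2. Following a serious, unexpected event ticked as unassessable**

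- Under the 11.2 grouping it is unrelated, so it is not a SUSAR.
- The 7- and 15-day notification in 11.6 covers SUSARs, so the event is not notified by that route.
- The forwarding to the manufacturer in 11.5 covers SUSARs, pregnancies and medication errors, so the event is not forwarded as a SUSAR.
- Whether pharmacovigilance receives it depends on which statement in 11.5 governs. If only related and unexpected events are sent, it need not be sent. If all serious adverse events are reported, it arrives but is still classed as unrelated for expedited notification.

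**3. Comparing the two deadlines**

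Inputs: 24 hours or one business day (11.5), and 24 hours after knowledge (Annex II). The protocol does not define a business day. I assume a Monday-to-Friday week and count to the same clock time on the next business day.

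Limit in hours = 24 × number of calendar days to the next business day.

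| Investigator learns on | Annex II | One business day | One business day, following Monday a holiday |
|---|---|---|---|
| Monday to Thursday | 24 | 24 × 1 = 24 | 24 |
| Friday | 24 | 24 × 3 = 72 | 24 × 4 = 96 |
| Saturday | 24 | 24 × 2 = 48 | 24 × 3 = 72 |
| Sunday | 24 | 24 × 1 = 24 | 24 × 2 = 48 |

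The equivalence stated in 11.5 holds from Sunday to Thursday and fails on two days of an ordinary week. The excess is 72 − 24 = 48 hours for Friday and 48 − 24 = 24 hours for Saturday. Counting to the close of the business day would add some hours. Because the clocks in 11.6 start at sponsor awareness, the excess comes before the 7 or 15 days begin. Elsewhere, 11.5 (medication errors) and 11.10 (pregnancy) use 24 hours with no business-day wording.

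**The case against.** The opposing case has several sound parts.

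- **An unassessable event does not fit the related class either.** This stands. Moving the category without touching the definitions would exchange one mismatch for another, so the definitions need aligning too. Grouping by default is partly a choice of convention, but the present choice is the less protective one and no reason is given for it.
- **A reader might infer that such events never reach the safety system.** The documents do not support this. Section 11.5 also says without a relatedness condition that serious adverse events should be reported. The form has boxes for improbable, excluded and unassessable causality, which would have little use if only related events were sent. Pharmacovigilance staff may ask for more information, and the investigator must report a changed causality assessment. What remains is that 11.5 gives two scopes, and that under either one the event misses expedited notification while its rating stands.
- **A reader might infer that the safety objective is undercounted.** This does not follow. The grouping applies only to expedited notification, and the safety endpoint in 6.1.2 covers the frequency, severity and relationship of any adverse event. Section 11.4 limits systematic collection to related events, but that is a separate matter and does not come from this grouping.
- **Other safety routes exist.** Section 11.7 requires notification within 15 days of information that could change the benefit/risk ratio, and 11.11 requires annual reports. Neither is a case-by-case expedited report of the event.
- **The business-day wording may be a loose gloss.** That is possible. It still permits more than 24 hours and disagrees with the form.

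**Conclusion.** The point holds as a defect in the safety-reporting rules. Section 11.2 treats unassessable events as unrelated for expedited notification, although they do not satisfy its own definition of unrelated and do not clearly satisfy that of related. A serious unexpected event with this rating is therefore not handled as a SUSAR: it misses the 7/15-day notification in 11.6 and the SUSAR forwarding in 11.5. Its arrival at pharmacovigilance is uncertain because 11.5 contradicts itself on scope.

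The size on the causality side is one of six rating categories. The protocol gives no basis for estimating how many events this would be in a trial planned for 37 patients. On the deadline side, the limit is 72 hours instead of 24 from a Friday and 48 instead of 24 from a Saturday, assuming a Monday-to-Friday week without holidays. The sample size, power and primary analysis are unaffected.

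**What to change.** - **Section 11.2:** for expedited notification, group events that cannot be assessed with the related ones until further information allows reclassification. Align the two definitions so that the category has a stated place.
- **Section 11.5, deadline:** remove the business-day gloss so that it gives the same 24 hours as Annex II.
- **Section 11.5, scope:** reconcile the two statements and say whether all serious adverse events or only SUSARs go to pharmacovigilance.

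The cost is a few wording changes and possibly a few more expedited reports, some of which would later be reclassified as unrelated.
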